**Table 2. SPIRIT Depiction of Timing and Measures Collected for Train-the-Trainer Phase**

[figure not shown]
	Screening	Post-Training	Pre-Treatment	Mid-Treatment	Weekly During Treatment	Post-Treatment †	6-Months Post-Treatment
Generation 2 Patient							
Sociodemographics			x			x	x
Eligibility Items	x						
PROMIS-SD P	x		x	x		x	x
PROMIS-SRI			x			x	x
DSM-5 Cross-Cutting			x			x	x
SDS			x			x	x
Sleep Health Composite			x			x	x
PHENX Toolkit			x			x	x
CEQ						x	
Generation 2 Provider							
Sociodemographics		x					
Occupation		x					
Acceptability P		x				x	
Appropriateness		x				x	
Feasibility		x				x	
Weekly Session Log					x		

*Note.* Allocation to Adapted or Standard TranS-C occurs at the county level and prior to enrollment of any participants in that county (i.e., patients or providers). Enrollment of patients and allocation to immediate TranS-C or delayed TranS-C (UC-DT) occur after the screening and before the pre-treatment assessment. Enrollment of providers occurs after the training; note: providers may hold a dual role as a local trainer. †Post-treatment assessments for immediate TranS-C and delayed TranS-C (UC-DT) were identical except that the CEQ was not delivered at the UC-DT post-treatment assessment. P = Primary Outcome. PROMIS-SD = PROMIS-Sleep Disturbance; note: PROMIS-SD is only assessed during the pre-treatment assessment if done more than one month after the screening to minimize burden for patients. PROMIS-SRI = PROMIS-Sleep Related Impairment. SDS = Sheehan Disability Scale. CEQ = Credibility/Expectancy Questionnaire.

[figure not shown]

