report and confirmed by referring provider or administration of the Mini International Neuropsychiatric Interview (DSM-5, Version 7.0.0) by a licensed clinical social worker on the research team; 3) exhibit a sleep or circadian disturbance as determined by endorsing 4 (quite a bit) or 5 (very much), or the equivalent for reverse scored items, on one or more PROMIS-Sleep Disturbance questions (54,55); 4) guaranteed place to sleep for at least two months that is not a shelter; 5) receiving the standard of care for the SMI and consent to regular communications between the research team and provider; and 6) consent to access their medical record and participate in assessments.

Patients will be excluded if they meet any of the following criteria: 1) presence of an active and progressive physical illness or neurological degenerative disease that is directly related to the onset and course of the sleep and circadian problems, or making participation in the study unfeasible, as assessed by the Checklist of Medical Conditions and Symptoms on the Duke Structured Interview for Sleep Disorders (56) and clinical interview; 2) presence of substance abuse/dependence only if it makes participation in the study unfeasible; 3) current active intent or plan to commit suicide (those with suicidal ideation are eligible) only if it makes participation in the study unfeasible, or homicide risk; 4) night shift work for more than two nights per week in the past three months (i.e., regularly scheduled work from 12 a.m. – 6 a.m.); or 5) pregnant or breastfeeding.

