### **3.6 Procedure**

Providers and patients are consented by the assessment team prior to participation. Although we do not collect trainer-specific data from local trainers, note that all trainers were required to complete a Generation 1 training, after which they had provided consent to participate. All participants are informed that they can withdraw from the study at any time. All patients are compensated for their participation, and providers are compensated if permitted by their CMHC. Local trainers volunteered to become trainers and were not compensated, however a certification in TranS-C training and a mug were provided if the trainer trained a minimum of 15 people across at least two trainings and supervised a minimum of three TranS-C cases.

Generation 2 provider and patient assessments are completed by the assessment team, comprised of experienced assessors. Note that assessors complete the consent process to minimize burden on participants (e.g., this practice reduces number of calls from team). Because the assessors need to provide study-related information—such as number of assessments and treatment sessions—to the patients during the consent process, the assessors are not blind to condition at the pre-treatment assessment. However, at post-treatment and 6FU, we endeavor to keep assessors blind to condition. As is common in clinical trials, there are ways that assessors may be able to infer treatment condition (e.g., slightly different assessment batteries, patients may ask assessors “when does treatment start?” during the post-delay assessment). Assessors receive ongoing supervision and are thoroughly trained to deliver the surveys with integrity and minimal bias.

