## **4 PLANNED ANALYSES**

### **4.1 Preliminary Analyses and Missing Data**

All analyses below pertain to the TTT Phase and are limited to Generation 2 providers and Generation 2 patients, except Exploratory Aim 1. For the primary analyses, which use multilevel modeling (MLM) and structural equation modeling, analyses will use all available data (intent-to-treat) (84). Models will be estimated with maximum likelihood estimation, and missing data will be assumed to be missing at random (85). For exploratory analyses using linear regression, approaches to missing data will be based on the number of missing cases (e.g., listwise deletion versus multiple imputation) (86). If dropout is related to other variables, they will be included as predictors. Baseline between-group differences in demographic variables will be examined. These tests will not be used to select covariates in the primary intention-to-treat analysis (87–90). Instead, covariates will be carefully selected at the conclusion of the trial—given the variations due to COVID-19 and the CMHC context (see Discussion)—and the potential influences of baseline differences will be evaluated as moderators (approach to moderation described below). Analyses comparing TranS-C to UC-DT will evaluate change in outcomes from pre-treatment to post-treatment. Analyses comparing Adapted to Standard TranS-C will evaluate change in Generation 2 outcomes from pre-treatment to post-treatment and pre-treatment to 6FU (see Method and Discussion for more details).

Distributions will be evaluated to detect outliers, and we will ensure that the assumptions of planned analyses are met. Covariates will include the patient variables for which we stratified (i.e., age and presence of psychosis or substance use). For all statistical models, counties will be adjusted for as a factor

variable rather than a level of analysis due to the relatively small number of clusters. The average intraclass correlation on provider and patient level outcomes will be reported.

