#### **4.3 Aim 1: Effectiveness Outcomes of Standard or Adapted TranS-C versus UC-DT**

Multilevel modeling (MLM) (91–93) will be used to account for multiple observations nested within patient. The level 1 equation will include dummy-coded time indicators as the predictor (0 = pre-treatment, 1 = post-treatment). The level 2 equation will include dummy-coded treatment condition (0 = UC-DT, 1 = Adapted or Standard TranS-C) and treatment by time interaction terms as predictors, adjusting for county. The treatment effects of interest will be significant treatment by time interactions at the 5% level on the primary outcome of sleep disturbance and the secondary outcomes of sleep-related impairment, functional impairment, and psychiatric symptoms, all modeled as continuous variables. Significant treatment by time interactions indicate that change in Generation 2 patient outcomes is significantly different comparing Adapted or Standard TranS-C to UC-DT. Significant interactions will be interpreted using planned contrasts (i.e., treatment effects on change from pre-treatment to post-treatment) and graphs. Additionally, the indirect effects of TranS-C relative to UC-DT on functional impairment and psychiatric symptoms through improvements in sleep disturbance and sleep-related impairment will be tested using multilevel structural equation modeling (94).

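### Aim 1's treatment-by-time test is valid but leaves the baseline score unadjusted, at an uncertain cost in precision, and the time-0 PROMIS-SD is implied rather than stated

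*Combined protocol and SAP*

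**What the plan says.** Section 4.3 codes time as 0 (pre-treatment) and 1 (post-treatment), includes a treatment term and its product with time, and adjusts for county. The criterion is: "The treatment effects of interest will be significant treatment by time interactions at the 5% level on the primary outcome of sleep disturbance". Section 4.1 describes the same quantity: "Analyses comparing TranS-C to UC-DT will evaluate change in outcomes from pre-treatment to post-treatment".

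On covariates, Section 4.1 says "Covariates will include the patient variables for which we stratified (i.e., age and presence of psychosis or substance use" and enters county as a factor. It also says that "covariates will be carefully selected at the conclusion of the trial". Baseline symptom scores appear as predictors only in the moderator models of Section 4.9.

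On the time-0 score, the note to Table 2 says "Enrollment of patients and allocation to immediate TranS-C or delayed TranS-C (UC-DT) occur after the screening and before the pre-treatment assessment", and that "PROMIS-SD is only assessed during the pre-treatment assessment if done more than one month after the screening". Every enrolled patient has a screening score, because eligibility in Section 3.2 requires a high rating, "or the equivalent for reverse scored items, on one or more PROMIS-Sleep Disturbance questions".

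**The concern.** A difference in mean change subtracts the whole baseline score from the outcome. Regression on baseline subtracts only the part that predicts the outcome, so in large samples it is never less precise and is usually more so. Section 3.8 says that timeframe and budget set the sample, so precision cannot be bought with more patients. The data for an adjusted estimate are already collected.

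The second issue is one of definition. Patients whose pre-treatment visit falls within a month of screening have no pre-treatment PROMIS-SD, yet the model needs a time-0 value. If the screening score stands in, time 0 precedes allocation for some patients and follows it for others. By the later visit patients know whether treatment is immediate or delayed (Section 3.2), and "the assessors are not blind to condition at the pre-treatment assessment" (Section 3.6).

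At stake are the width of the confidence interval for the primary patient effect and the clarity of its baseline. No planned conclusion becomes wrong.

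**Working it through.** **1. The plan's own figure.** Section 3.8 gives a minimum detectable d = 0.94 for 130 patients, 9 clusters, ICC 0.30, coefficient of variation 0.72 and two-sided alpha 0.05; power is not stated, so 80% is assumed here. Formula: d = 2.80 × √(2·DE/n per arm), with DE = 1 + ((CV² + 1)m − 1)·ICC.
- 65 per arm, m = 130/9 = 14.44: DE = 7.28, d = 1.33.
- 65 per arm, each county feeding both arms, m = 7.22: DE = 3.99, d = 0.98.
- 130 per arm, m = 14.44: d = 0.94.

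So 0.94 is not recovered from 130 patients in total. That is a separate matter. What counts here is that no pre-post correlation enters the figure, and none can be extracted from it. The correlations of .37 to .39 in Section 3.8 relate treatment to outcome, not pre to post.

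**2. Formulas.** Let r be the pre-post correlation and s the ratio of baseline SD to post-treatment SD, both within county and stratum. In units of post-treatment variance:
- planned interaction, complete data: 1 + s² − 2rs
- adjusted for baseline: 1 − r²
- proportional saving: (s − r)² / (1 + s² − 2rs)

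Example, s = 1, r = .5: .25/1.00 = 25%.

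If a fraction f of post scores is observed and maximum likelihood uses every baseline, the saving is f(s − r)² / (1 − r² + f(s − r)²). At f = .8 (assumed), s = 1, r = .5: .20/.95 = 21%.

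| Saving: complete data (20% missing) | r = .2 | r = .5 | r = .8 |
|---|---|---|---|
| s = 1 | 40% (35%) | 25% (21%) | 10% (8%) |
| s = .8 | 27% (23%) | 11% (9%) | 0% (0%) |
| s = .6 | 14% (12%) | 1% (1%) | 10% (8%) |

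A ratio below 1 is plausible because patients are selected on PROMIS-SD items at screening.

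**3. Do the named covariates recover the loss?** No. A time-constant main effect cancels from within-patient change. In one simulated complete data set of 130, the interaction was −0.3994 (SE 0.1713) both with and without terms for nine counties and three strata. Adding the baseline score itself as a main effect to the two-row model also left the interaction unchanged, so the form of the model has to change. With 20% of post scores missing, the covariates left the mean SE the same to three decimals (0.205 at r = .4; 0.169 at r = .6).

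**4. Correction for 130 patients.** ANCOVA pays for its covariates. Eight county contrasts, three stratification terms and the baseline make 12 terms, and chance imbalance inflates the variance by roughly (130 − 3)/(130 − 12 − 3) = 127/115 = 1.10. The planned contrast does not pay this, because its covariates cancel.
- s = 1, r = .5: 0.75 × 1.10 = 0.83, a saving of 17%. Simulations with assumed county sizes gave 17% and about 15%.
- s = .8, r = .5: 0.893 × 1.10 = 0.99, a saving of about 1%. Simulations gave 6% and about 2%.
- s = r: no saving to offset the inflation, so variance rises by up to about 10% (√1.10 = 1.05, an interval about 5% wider).

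**5. Screening score against a newer score.** For re-measured patients the planned model may use the newer score. Suppose equal SDs and a newer-score r of .70. Planned change then has factor 2(1 − .70) = 0.60. ANCOVA on the screening score has 1 − .50² = 0.75 if its r is .50 (25% worse), or 1 − .60² = 0.64 if its r is .60 (7% worse). Break-even is √(1 − 0.60) = .63.

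**6. Validity.** Simulated type I error with r = .5, 130 patients, no effect, and s = 1, .8, .6:

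| Model | Complete data | 20% missing |
|---|---|---|
| Planned interaction, random intercept (assumed form) | 5.7%, 5.1%, 5.4% | 5.5%, 6.4%, 6.8% |
| ANCOVA | 5.1%, 5.0%, 5.1% | 4.5%, 5.1%, 4.9% |
| Common baseline mean, unstructured covariance | 5.6%, 5.7%, 5.7% | 5.1%, 5.7%, 5.6% |
| Common baseline mean, random intercept | 5.6%, 8.2%, 11.8% | 5.0%, 8.5%, 11.8% |

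The last row should be avoided.

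**The case against.** The strongest reply is that nothing here is an error. Change from pre- to post-treatment is a legitimate quantity, stated in two places and chosen to parallel the Implementation Phase (Section 2). Every r and SD above is assumed. The Discussion treats the sample as possibly sufficient for Aim 1, and Section 3.8 cites a prior effect of d = 0.96. At that effect, with 104 completers, individual randomisation and equal arms assumed, the planned contrast has power of 97% or more for r = .2 to .5 and s = .8 to 1. The reply stands. Adjustment matters more if the effect is about half as large: at d = 0.5, large-sample power goes from 52% to 74% (r = .2, s = 1) or from 79% to 84% (r = .5, s = .8), before the correction in step 4.

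It can also be said that the Table 2 note has a natural reading, namely that a recent screening score stands in for the pre-treatment one. That is fair, and it makes this part a clarification.

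Four stronger readings are tempting and are not supported:
- That the planned test is biased or invalid. Randomisation protects it.
- That mixing pre- and post-allocation scores biases the result. The possibility exists, but no document shows that it happened or in which direction.
- That the table gives the gain from adopting the screening score. It assumes one baseline in both analyses; step 5 shows that the change can lose precision for re-measured patients, whose share is unknown.
- That naming the baseline score settles the deferred covariates. Delivery and supervision format (Section 5) would stay open.

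**Conclusion.** The point holds as one of efficiency and definition. Aim 1's interaction is valid but unadjusted for baseline, and the covariates named in Section 4.1 do not make up the difference. The large-sample variance saving with one common baseline is 0% to 40% over the assumed range. With 130 patients and the planned county and stratum terms it is about 15% at s = 1, r = .5 and about 2% at s = .8, r = .5, and it can vanish or reverse slightly when s is close to r. These figures assume individual randomisation within county and equal missingness by arm. They cannot be set against d = 0.94, which comes from a cluster-randomised formula. The time-0 rule is implied but unwritten, and no bias from it is shown.

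**What to change.** In a dated amendment, made before any outcome analysis by arm:
- Add a baseline-adjusted estimate of the post-treatment TranS-C minus UC-DT difference. Use ANCOVA, or a common-baseline-mean model with unstructured covariance. Keep county, the stratification factors and all available data, and report the planned interaction beside it.
- State one time-0 rule for both arms.
- Use the pre-allocation screening PROMIS-SD as the adjustment baseline. Repeat with the most recent pre-treatment score as a sensitivity analysis, and report the share re-measured by arm.
- For PROMIS-SRI, SDS and the DSM-5 measure, first taken after open allocation, present the adjusted estimate as supporting only.
- If outcomes by arm have already been seen, present the adjusted PROMIS-SD estimate as supporting too.

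The cost is one extra model per outcome and no new data. The change is late: Section 6 dates version 1 to May 2023, with assessments running through August 2023. Under Section 3 it goes to the registry and the ethics committee, and it should say who had seen outcomes by arm. Section 3.9 describes interim summaries for site leadership but says that they do not address the aims. The reported quantity moves from difference in change to adjusted post-treatment difference; with a pre-allocation baseline both estimate the same effect. The main downside is little or no gain if the screening score is older and less correlated with outcome.

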The first aim is to assess the effectiveness of TranS-C, compared to UC-DT, in patients who are treated by Generation 2 providers. We hypothesize that, compared to UC-DT, TranS-C (combined Adapted and Standard) will be associated with larger reductions in the primary patient outcome of sleep disturbance and the secondary patient outcomes of sleep-related impairment, functional impairment, and psychiatric symptoms. We also hypothesize that TranS-C’s benefits for functional impairment and psychiatric symptoms will be mediated by improvements in sleep and circadian problems. The second aim is to evaluate whether TranS-C treatment condition (Adapted vs. Standard TranS-C) is associated with fit to the CMHC context, operationalized as provider ratings of acceptability, appropriateness, and feasibility, for Generation 2 providers. We hypothesize that Adapted TranS-C will be superior to Standard TranS-C with respect to the primary provider outcome of acceptability and the secondary provider outcomes of appropriateness and feasibility. The third aim is to evaluate whether perceived fit among Generation 2 providers mediates the relation between TranS-C treatment condition and Generation 2 patient outcomes. We hypothesize that relative to Standard TranS-C, Adapted TranS-C will be associated with greater reductions in the primary and secondary patient outcomes indirectly through higher provider ratings of acceptability, appropriateness, and feasibility. Exploratory analyses will: (1) compare whether the effectiveness of TranS-C for primary and secondary patient outcomes is moderated by generation, (2) compare Adapted and Standard TranS-C on Generation 2 patient perceptions of credibility and perceived improvement and select PhenX Toolkit outcomes that are both strongly related to SMI and sleep and circadian problems (e.g., substance use, suicidality) (43–46) and of high priority to our community partners; and (3) determine whether treatment effects for Generation 2 patients are moderated by risk factors including age, sex, and sleep and circadian and psychiatric symptoms at baseline. In particular, emerging evidence suggests that patients who are older and have more severe sleep and circadian and psychiatric symptoms at baseline demonstrate poorer response to sleep and circadian treatment, whereas outcomes by sex have been mixed for patients with SMI (47,48).

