##### 3.5.2.2 Secondary Outcomes

*Sleep-Related Impairment.* The 16-item PROMIS-Sleep Related Impairment (PROMIS-SRI) assesses

daytime impairment related to sleep problems over the past seven days on a scale from 1 (not at all/never) to 5 (very much/always) (54). Scores range from 16-80, with higher scores indicating greater impairment (e.g., daytime sleepiness, difficulty concentrating). This measure has demonstrated excellent psychometric properties (54,55).

*Functional Impairment.* Functional impairment is assessed via the Sheehan Disability Scale (SDS) (68). Impairment in work and school, social life, and home and family is rated on a scale from 0 (not at all) to 10 (extremely). Scores range from 0-30, with higher scores indicating greater impairment. This measure has demonstrated good reliability and validity (68,69).

*Overall Sleep Health.* The Sleep Health Composite is proposed to capture overall sleep health for the complexity of sleep problems in SMI that are covered by TranS-C (70). It is defined as the sum of scores on six sleep health dimensions (each dimension dichotomized as 1 = good; 0 = poor): Regularity (midpoint fluctuation), Timing (mean midpoint), Efficiency (sleep efficiency), Duration (total sleep time), Satisfaction (sleep quality question on PROMIS-SD), and Alertness (daytime sleepiness question on PROMIS-SRI). All dimensions – except Satisfaction and Alertness – are assessed via questions about sleep-wake patterns over the past seven days (e.g., In the past week, what time have you usually woken up in the morning?). Scores range from 0-6, with higher scores indicating better sleep health. Initial validity of this measure has been established (70).

*Psychiatric Symptoms.* The DSM-5 Cross-Cutting Measure assesses psychiatric symptoms across 13 mental health domains. Participants rate how often they were bothered by each symptom on a scale from 0 (not at all) to 4 (nearly every day). Scores range from 0-52, with higher scores indicating more severe symptoms. This measure has demonstrated good test-retest reliability and clinical utility (71,72).

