#### ***3.6.3 Generation 2 Patients***

Patient assessments in the immediate TranS-C treatment conditions are completed at pre-treatment, mid-treatment, post-treatment, and six months after treatment (6FU). Patient assessments in the UC-DT condition are completed at pre-treatment and four or eight weeks after pre-treatment (i.e., post UC-DT), depending on whether their county has been randomized to Adapted or Standard TranS-C, respectively. After the post UC-DT assessment, patients start delayed treatment with TranS-C. They subsequently complete assessments at mid-treatment, post-treatment, and 6FU. Note that patients do not complete a

6FU assessment after the delayed portion of UC-DT. This was a compromise made with CMHC partners, so that patients would not need to wait 7-8 months to receive treatment. See Figure 2 for patient timeline.

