The potential contributions of this protocol must be considered alongside its methodological limitations. First, given real-world factors, particularly the COVID-19 pandemic, our sample size is unlikely to be optimal and analyses may be underpowered. That said, estimates of the minimum detectable effect size presented above suggest that the anticipated sample sizes for providers and patients may be sufficient for Aim 1 and we will use effect sizes in conjunction with p-values to interpret the findings for Aims 2 and 3. Additionally, relative to the existing TTT literature in CMHCs, the current estimated sample for both providers and patients is substantial (8). Nonetheless, it is crucial for future research to examine TTT with larger samples to allow for more sophisticated analyses on the multitude of factors that may influence TTT outcomes.

Second, to reduce burden on our CMHC collaborators, we did not collect data from leadership nor local trainers at our partner CMHCs about their perceptions or feedback on TTT. We recognize that leadership-level factors can meaningfully impact implementation outcomes (104). Therefore, exploring leadership perspectives on TTT and TranS-C is an important direction for future research. Additionally, very few studies have collected data from local trainers (21). Thus, this area is ripe for both qualitative and quantitative research on a range of factors, such as local trainer attributes, effectiveness, competence, and perceptions of barriers and facilitators to sustaining the EBPT.

Third, as is common in TTT studies, our follow-up period is relatively brief (i.e., 6FU of TranS-C). It would be informative for future research to monitor outcomes over several generations of trainers and supervisors to provide robust tests of long-term TTT sustainability. Additionally, in the UC-DT condition, patients did not complete a 6FU assessment after the delay, and we did not collect 6FU data from providers. These were compromises made with CMHC partners to reduce burden and maximize participation in the study. Increasing our follow-up period to study the long-term effects of TranS-C relative to a control (e.g., UC-DT) and Generation 2 providers' perceptions of TranS-C will be important directions for future research.

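### The Aim 1 sleep-mediation test rests on a same-interval, non-randomised association, and nothing planned shows how much confounding of sleep change and outcome change would overturn it

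*Combined protocol and SAP*

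**What the plan says.** Section 2 states the hypothesis causally: TranS-C's "benefits for functional impairment and psychiatric symptoms will be mediated by improvements in sleep and circadian problems". Section 4.3 tests it by multilevel structural equation modelling, as the "indirect effects of TranS-C relative to UC-DT on functional impairment and psychiatric symptoms through improvements in sleep disturbance and sleep-related impairment". It gives no path timing, no assumption about confounding and no decision rule for the indirect effects.

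The timing follows from other sections:

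- Section 4.1: "Analyses comparing TranS-C to UC-DT will evaluate change in outcomes from pre-treatment to post-treatment".
- Section 3.6.3: "Patient assessments in the UC-DT condition are completed at pre-treatment and four or eight weeks after pre-treatment". Delayed treatment starts after the second of these visits. The mid-treatment visit belongs to the treated period.
- Section 5: "in the UC-DT condition, patients did not complete a 6FU assessment after the delay".

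Planned adjustment covers county and the patient stratification variables, with further covariates to be chosen at the end of the trial (sections 4.1 and 5). The three sets of sensitivity analyses in section 4.6 concern the number of sessions attended, substitution of mid-treatment scores, and late assessments. One of the two mediators, PROMIS-SRI, is described in section 3.5.2.2 as a measure of "daytime impairment related to sleep problems over the past seven days".

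**The concern.** Only the path from treatment to sleep is protected by randomisation. The path from sleep to functioning or psychiatric symptoms compares patients within arm on two sets of questionnaire answers covering the same weeks. Mood, life events or response style could move both. So could a change in functioning that affects sleep.

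The product of the two paths is zero only if one of them is zero. When the treatment effect on sleep is large, the first path is rarely in doubt, and the result depends on whether sleep change and outcome change are correlated within arm. That is a weaker statement than the one in section 2. At stake is the trial's conclusion about mechanism, namely whether improving sleep is what improves functioning. The treatment-by-time results of Aim 1 are not affected.

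**Working it through.** **Inputs.** From section 3.8: 130 patients, 9 counties, d = 0.94 as the minimum detectable effect and 0.96 in the prior trial. County enters as a factor (sections 4.1 and 4.3).

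Assumptions, because the documents do not state them for this test:
- 1:1 patient allocation.
- d expressed in standard deviations of change.
- A 95% interval for the indirect effect, as in the Aim 3 power calculation.
- 104 patients as a loss scenario, applying the 20% attrition of the earlier combined-phase target (130 × 0.8 = 104).
- Residual within-arm correlation r of the two changes varied, since no figure is given. The 0.50 in section 3.8 concerns provider fit and patient outcome, so it cannot fill this gap.

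**Method check.** The documents' only mediation power figure is 0.62 for Aim 3 (60 providers; correlations 0.30, 0.50 and 0.20). A Monte Carlo interval for the product of paths gives 0.63, so the method is reproduced.

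**Hand calculation, no causal sleep path.** The indirect effect is declared when both paths are clear of zero.

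- Path a (treatment to sleep): expected statistic d√N/2 = 0.94 × 11.40/2 = 5.36. The chance of exceeding 1.96 is Φ(3.40), above 99.9%.
- Path b (sleep to outcome, adjusted for arm and county, 11 coefficients): expected statistic r√(N − 11)/√(1 − r²), with √119 = 10.91.
  - r = 0.1: 1.10, chance Φ(−0.86) = 19%.
  - r = 0.2: 2.23, chance Φ(0.27) = 61%.
  - r = 0.3: 3.43, chance Φ(1.47) = 93%.
- With N = 104, √93 = 9.64. At r = 0.2 the statistic is 1.97 (50%); at r = 0.3 it is 3.03 (86%).

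**Simulation.** Change scores, county indicators, Monte Carlo interval, true sleep-to-outcome effect zero, total effect on functioning zero. Repeat runs agree within a few points.

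| Effect on sleep | N | r = 0.1 | r = 0.2 | r = 0.3 | r = 0.4 |
|---|---|---|---|---|---|
| d = 0.94 | 130 | 20% | 61% | 93% | 99% |
| d = 0.94 | 104 | 16% | 53% | 83% | 98% |
| d = 0.5 | 130 | 14% | 45% | 71% | 79% |

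At d = 0.3 the rate is at most 40% for any r up to 0.5. At r = 0 it is nominal, including when TranS-C has a direct effect of 0.4 on functioning.

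**Can the output tell the cases apart?** At d = 0.94 and r = 0.3 with no causal path, the mean indirect effect is 0.94 × 0.3 = 0.28 SD. A true path of b = 0.3 with r = 0 gives the same 0.28 SD and is detected in about 90% of trials. The indirect effect alone does not distinguish them.

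**The case against.** Several points on the other side stand.

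- **Direct action on functioning is handled.** A reader might infer that the model cannot separate mediation through sleep from TranS-C acting on both sleep and functioning. That is not so. Path b is adjusted for arm, and at r = 0 the rate is nominal even with a direct effect. Only correlation left over within arm misleads.
- **The result is conditional.** A reader might infer that any correlation would be read as mediation, or that a positive finding is close to guaranteed. The documents give no residual correlation, and at r = 0.1 or with d = 0.3 most trials would not report mediation. The 0.94 is a minimum detectable effect, and the 0.96 comes from university-based therapists (section 1). Section 1 also cites evidence of poorer outcomes in Generation 2. Section 3.8 does, however, call an effect of this size feasible to detect.
- **A missing benefit would usually be visible.** Section 4.3 also tests the total effect on functioning and symptoms. With no true benefit, that test is non-significant in about 95% of trials, and the estimated direct effect would be about 0.28 SD in the opposite direction to the indirect effect (d = 0.94, r = 0.3). This does not help where functioning improves by another route. With a direct effect of 0.4, no causal sleep path and r = 0.3, mediation is still reported in more than 90% of trials.
- **A significant total effect is a costly gate.** It would cut false reports to about 3% or less in the no-benefit case at d = 0.94. It would also cut detection of a true path of b = 0.3 from about 90% to 29%.
- **The limitation is common to two-visit mediation, and this is a supplementary test.** That bears on its weight. The hypothesis is nevertheless stated explicitly in section 2, and no assumption or check accompanies it.

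**Conclusion.** The concern holds in conditional form. The randomised contrast holds no data that would place sleep change before outcome change, and no planned analysis addresses mediator-outcome confounding. If the within-arm residual correlation is about 0.2 to 0.3 or more and the effect on sleep is near d = 0.94, most trials would report mediation with no causal sleep path: 61% and 93% with 130 patients, 53% and 83% with 104. At d = 0.5 the figures are about 45% and 71% with 130 patients.

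These rates rest on 1:1 allocation, a single-level change-score equivalent of the two-visit model, and one mediator-outcome pair at a time. The documents do not support a claim that false mediation is the usual outcome. The overlap of PROMIS-SRI with the Sheehan Disability Scale (SDS) is one of content and concerns one of the four pairs. It calls for careful reading of that pair and does not require dropping the mediator.

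**What to change.** In section 4.3:

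1. For each indirect effect, add a sensitivity analysis over the mediator-outcome residual correlation, for example 0 to 0.5. Report the value at which the estimate reaches zero and the value at which its 95% interval first includes zero. As a rough guide with 130 patients, an observed within-arm correlation of 0.3 has standard error 0.954/10.91 = 0.087, so the interval would first include zero near 0.3 − 1.96 × 0.087 = 0.13.
2. Word the conclusion as mediation conditional on no mediator-outcome confounding beyond that value; otherwise describe an association between sleep change and outcome change. The analysis cannot show which explanation is true. It shows how much confounding the claim can bear.
3. Report each indirect effect beside the total and direct effects, without making a significant total effect a condition.
4. Note the content overlap when reading the PROMIS-SRI to SDS pair.
5. Optionally, relate pre- to mid-treatment PROMIS-SD change to later post-treatment SDS and DSM-5 scores in treated patients, labelled as non-randomised support. Table 2 collects only PROMIS-SD at mid-treatment, so concurrent outcome change cannot be adjusted for.

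The cost is SAP wording and a few extra model runs on data already planned, with no new visits or patients. The downside is that fewer results will be described as confirmed mediation.
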